Appendix C (The IRB-approved Protocol)

	Home	Outdoor area at home	Other residence (ex. babysitter's house)	Store	Restaurant	Church	Other indoor location	Park	Bus/train stop	On or near street	Parking garage	Other outdoor location	In vehicle	Don't know/Refused to answer
10:00 am - 10:29 am														
10:30 am - 10:59 am														
11:00 am - 11:29 am														
11:30 am - 11:59 am														
12:00 pm - 12:29 pm														
12:30 pm - 12:59 pm														
1:00 pm - 1:29 pm														
1:30 pm - 1:59 pm														
2:00 pm - 2:29 pm														
2:30 pm - 2:59 pm														
3:00 pm - 3:29 pm														

Appendix C (The IRB-approved Protocol)

	Home	Outdoor area at home	Other residence (ex. babysitter's house)	Store	Restaurant	Church	Other indoor location	Park	Bus/train stop	On or near street	Parking garage	Other outdoor location	In vehicle	Don't know/Refused to answer
3:30 pm - 3:59 pm														
4:00 pm - 4:29 pm														
4:30 pm - 4:59 pm														
5:00 pm - 5:29 pm														
5:30 pm - 5:59 pm														
6:00 pm - 6:29 pm														
6:30 pm - 6:59 pm														
7:00 pm - 7:29 pm														
7:30 pm - 7:59 pm														
8:00 pm - 8:29 pm														
8:30 pm - 8:59 pm														

Appendix C (The IRB-approved Protocol)

	Home	Outdoor area at home	Other residence (ex. babysitter's house)	Store	Restaurant	Church	Other indoor location	Park	Bus/train stop	On or near street	Parking garage	Other outdoor location	In vehicle	Don't know/Refused to answer
9:00 pm - 9:29 pm														
9:30 pm - 9:59 pm														
10:00 pm - 10:29 pm														
10:30 pm - 10:59 pm														
11:00 pm - 11:29 pm														
11:30 pm - 11:59 pm														

Appendix C (The IRB-approved Protocol)

4. Look back at the answers to question 3. Based on yesterday's day of the week, do these locations represent a fairly typical or normal day for your child? For example, if yesterday was a weekday, is this a typical weekday schedule for your child?

- Yes
- No
- Don't know/Refused to answer

Appendix C (The IRB-approved Protocol)

C. Activity Questions (To be completed by field technician and participant)

5. For each approximate time period given below, indicate activities your child performed. Select all that apply for the time period.

	Dress, groom or bathe	Eat	Watch TV	Play	Use computer or play video games	Read or do school work	Take care of younger children	Chores	Exercise	Play with pet	Arts and crafts	Sleep	Don't know/Refused to answer	None of these
5:00 am - 5:29 am														
5:30 am - 5:59 am														
6:00 am - 6:29 am														
6:30 am - 6:59 am														
7:00 am - 7:29 am														
7:30 am - 7:59 am														
8:00 am - 8:29 am														
8:30 am - 8:59 am														
9:00 am - 9:29 am														
9:30 am - 9:59 am														

Appendix C (The IRB-approved Protocol)

	Dress, groom or bathe	Eat	Watch TV	Play	Use computer or play video games	Read or do school work	Take care of younger children	Chores	Exercise	Play with pet	Arts and crafts	Sleep	Don't know/Refused to answer	None of these
10:00 am - 10:29 am														
10:30 am - 10:59 am														
11:00 am - 11:29 am														
11:30 am - 11:59 am														
12:00 pm - 12:29 pm														
12:30 pm - 12:59 pm														
1:00 pm - 1:29 pm														
1:30 pm - 1:59 pm														
2:00 pm - 2:29 pm														
2:30 pm - 2:59 pm														
3:00 pm - 3:29 pm														
3:30 pm - 3:59 pm														

Appendix C (The IRB-approved Protocol)

	Dress, groom or bathe	Eat	Watch TV	Play	Use computer or play video games	Read or do school work	Take care of younger children	Chores	Exercise	Play with pet	Arts and crafts	Sleep	Don't know/Refused to answer	None of these
4:00 pm - 4:29 pm														
4:30 pm - 4:59 pm														
5:00 pm - 5:29 pm														
5:30 pm - 5:59 pm														
6:00 pm - 6:29 pm														
6:30 pm - 6:59 pm														
7:00 pm - 7:29 pm														
7:30 pm - 7:59 pm														
8:00 pm - 8:29 pm														
8:30 pm - 8:59 pm														
9:00 pm - 9:29 pm														
9:30 pm - 9:59 pm														

Appendix C (The IRB-approved Protocol)

	Dress, groom or bathe	Eat	Watch TV	Play	Use computer or play video games	Read or do school work	Take care of younger children	Chores	Exercise	Play with pet	Arts and crafts	Sleep	Don't know/Refused to answer	None of these
10:00 pm - 10:29 pm														
10:30 pm - 10:59 pm														
11:00 pm - 11:29 pm														
11:30 pm - 11:59 pm														

Appendix C (The IRB-approved Protocol)

6. When at home, which room does your child sleep in?

- Child's bedroom
- Mother's bedroom
- Living room
- Other room in the home
- Don't know/Refused to answer

7. When indoors at home and awake, where does your child spend the most time?

- Living room/family room
- Child's bedroom
- Mother's bedroom
- Kitchen
- Other room in the home
- Don't know/Refused to answer

8. When at home, how much time per day does your child spend sitting/playing/lying on the floor?

- Less than 30 minutes
- 30 minutes
- 1 hr
- 1.5 hrs
- 2 hrs
- 2.5 hrs
- 3 hrs
- More than 3 hrs
- Don't know/Refused to answer

9. Is the floor she or he plays on carpeted?

- Carpeted
- Not carpeted
- Partially carpeted
- Child does not play/sit/lie on the floor
- Don't know/Refused to answer

Appendix C (The IRB-approved Protocol)

10. Typically, how much time per day does your child play outside at home (yard, common area, playground)?

- 0-15 minutes
- 15-30 minutes
- 30 minutes to 1 hour
- 1-2 hours
- 2-3 hours
- More than 3 hours
- Don't know/Refused to answer

11. Typically, how much time per day does your child play outside at school/daycare?

- 0-15 minutes
- 15-30 minutes
- 30 minutes to 1 hour
- 1-2 hours
- 2-3 hours
- More than 3 hours
- Don't know/Refused to answer

12. How much time per day does your child play at local parks?

- 0-15 minutes
- 15-30 minutes
- 30 minutes to 1 hour
- 1-2 hours
- 2-3 hours
- More than 3 hours
- Don't know/Refused to answer

13. How often does your child's sleep get interrupted (e.g., by noise or other disturbance in the community)?

- Never
- Once a month
- Once a week
- More than once a week
- Don't know/Refused to answer

Appendix C (The IRB-approved Protocol)

14. How many times did your child wash his/her hands yesterday?

- 1
- 2
- 3
- 4
- 5
- 6
- 7
- More than 7
- Don't know/Refused to answer

15. How many times a week does your child bathe?

- 1
- 2
- 3
- 4
- 5
- 6
- 7
- More than 7
- Don't know/Refused to answer

D. Diet Questions (To be completed by field technician and participant)

16. How many meals did your child eat yesterday (e.g., breakfast, lunch, dinner), not counting snacks?

- 1
- 2
- 3
- 4
- 5
- 6
- 7
- More than 7
- Don't know/Refused to answer

Appendix C (The IRB-approved Protocol)

17. For each MEAL your child ate, what best describes the meal? If your child ate more than 4 meals, just answer for the first 4.

	Meal prepared by school	Meal made at home from ready-made frozen or canned food	Fast food meal	Restaurant meal (not fast food)	Meal made at home from scratch	Don't know/Refused to answer
Meal 1						
Meal 2						
Meal 3						
Meal 4						

Appendix C (The IRB-approved Protocol)

18. On average, how often does your child eat/drink the following foods and beverages?

	Once a month or less	2-3 times per month	1-2 times per week	3-4 times per week	5-6 times per week	Once a day	2-3 times per day	4-5 times per day	6 or more times per day
Poultry									
Beef									
Pork									
Fish									
Shellfish									
Rice									
Other dairy products (not milk)									
Leafy green vegetables									
Other vegetables (not potatoes)									
Potatoes									
Breads									
Fruit									
Snack Foods									
Milk									
Fruit juice									
Soda									
Tap water or beverage made with tap water									

Appendix C (The IRB-approved Protocol)

19. How often do you purchase food at each of these types of stores?

	Never	Once a month	Once a week	2 times a week	3 times a week	More than 3 times a week
Supermarket or large grocery store						
Small grocery store (e.g., small store in your neighborhood that mainly sells food)						
Farmer's or outdoor market						
Store in a gas station						
Discount store (e.g., a dollar store, Big Lots)						

20. How often does your child eat at each of these types of restaurants?

	Never	Once a month	Once a week	2 times a week	3 times a week	More than 3 times a week
Fast food						
Sit - down restaurant						
Food truck or stand						

Appendix C (The IRB-approved Protocol)

E. Household Cleaning Products (To be completed by field technician and participant)

21. Please select use frequency for each product type inside your home

	Daily	Weekly	Monthly	Yearly/ Never
All-purpose cleaner				
Glass cleaner				
Floor cleaner				
Toilet bowl cleaner				
Carpet cleaner				
Polish or wax				
Air freshener				
Disinfectant Spray				
Laundry detergent				
Dryer sheets				
Stain/spot remover				

F. Personal Care Products (To be completed by field technician and participant)

22. Please select use frequency for each product type inside your home

	Daily	Weekly	Monthly	Yearly/ Never
Shampoo				
Liquid hand soap				
Hand sanitizer				
Hand/body lotion				
Facial moisturizer				
Fragrance/perfume				
Hair styling products				
Sunscreen				

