Appendix C (The IRB-approved Protocol)

4.4.1 Environmental Samples

Additional environmental samples will be collected for analysis of chemicals of interest to EPA. Collection of field samples will be carried out by trained technicians using standardized protocols. A quality assurance project plan (QAPP) and standard operating procedures will be prepared and approved prior to collection of field samples. Field staff will be trained by CDC and EPA personnel. Environmental samples will include indoor air, house dust, soil, and surface wipes.

An indoor air sample will be collected from the main play area in the home. Both passive and active air sample collection will be used. The active air sampling approach will use low volume air samplers placed in a childproof, sound-proof housing and located in the child's play area. The pump flow rate will be sufficiently low to ensure that the pump can run for 5 consecutive days with minimum disruption to the study participants. A polyurethane foam (PUF) filled glass tube will be combined with a quartz or Teflon particle filter for collecting semi-volatile target analytes. Passive air collection will be performed by deploying a sorbent tube diffusion sampler in the child's play area. The passive sampler will collect volatile target analytes. The tube cap will be removed on the first day of sampling, and will be replaced on the return visit on Day 5.

House dust samples will be collected from a floor (preference: carpeted surface; alternate: hard surface) where the children may play or spend time. House dust will be collected using a forensic vacuum equipped with an in-line filter to collect and trap surface dislodgeable particles. The sampled area will be measured, marked, and recorded to ensure accurate documentation of amount of available dust for chemical and biological analyses. If available, field technicians will collect a participant's household vacuum cleaner bag. A swiffer settled dust collection protocol will also be used to collect settled dust from the tops of door jambs and bookcases. Dust samples will also be collected from the aforementioned areas using an electrostatic dust collector (EDC). Two EDCs will be placed horizontally at surfaces at least 1.5 meters above the floor and exposed for five days.

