4.4.4 Accelerometer and GPS

Activity and location data will be collected from both the index child and sibling on Days 2-4 of the study using minimally burdensome technologies, namely a waistband-mounted accelerometer-based activity monitor (Actical™; Philips Respironics, Bend, Oregon) and a Global Positioning System (GPS) Data Logger (model BT-Q1000XT; Qstarz International, Taipei, Taiwan). Field study technicians will prepare the devices for data collection and instruct participants on placement and use of the devices. Both devices will be worn by study participants during awake periods for all three days; the final day of data collection will correspond to the day covered by the EPA pilot study add-on questionnaire (collected on Day 5; questions are answered by participants for activities and locations for the preceding day, i.e., Day 4). The Actical™ requires no recharging during the data collection period; the BT-Q1000XT Data Logger will require recharging by the study participant's caregiver each evening. The devices will be collected by the field technician on Day 5 and the collected data downloaded and stored. Figure 1 shows the data flow for the accelerometer and GPS data.

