Information on usage frequency of household cleaning products and personal care products will be collected as part of the questionnaire. These questions are based on participant recall and cover typical cleaning and personal care activities carried out by any of the household residents. This section consists of three parts: (1) questions on the use of products in nine consumer product categories; (2) questions on specific types of household cleaning products; and (3) questions on specific types of personal care products.

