Appendix C (The IRB-approved Protocol)

Objective	Measurements Required	Proposed Analysis Approach

5) Examine the relationships between consumer products in a residence, environmental concentrations, and exposure to active ingredients found in consumer product chemicals to support development and evaluation of models for predicting exposure to these chemicals
	
Household consumer product inventories, house dust, surface wipes, air, blood, urine concentrations
	
Quantification of relationships among media (dust, wipes, air) concentrations by chemical (correlations within and between subjects, descriptive statistics of ratio of air concentrations to surface concentrations); correlation between media (air and dust) concentrations and biomarker concentrations (within and between subjects by chemical); comparison of chemicals (individual or by class) in products found in the home with those found in dust and air (presence/absence) based on available databases of chemical ingredients; comparison of chemicals (individual or by class) in product categories reported as used in the home with those found in media (presence/absence, correlation of magnitude with reported use frequencies) based on available databases of chemical ingredients

6) Measure biomarkers of consumer product chemicals for young children in conjunction with environmental measurements to evaluate exposure and dose models
	
House dust, air, duplicate diet, blood, urine concentrations; activity information; survey information
	
Descriptive statistics; correlation analyses; uni- and multi-variate analyses for biomarker measurements; model runs (e.g., SHEDS, PBPK model, PROCEED) for forward/reverse dosimetry; comparison (t-test, correlations) between measurements and model predictions

7) Assess rapid, low burden, low cost methods for characterizing consumer product use in the residential environment to predict exposure to chemicals
	
Photographs of storage locations for household cleaning products and personal care products; barcode scanner inventory of products
	
EPA investigators will identify products in the photographs (blinded to scanner inventory). Image-based inventories will be evaluated against barcode-based inventories to assess collection accuracy (number of products correctly identified in photo divided by number in scanned inventory)

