EPA has recently developed new methods for predicting exposure to chemicals in consumer products. These methods are implemented in the Stochastic Human Exposure and Dose-Simulation Model – High Throughput (SHEDS-HT) human exposure model (Isaacs et al., 2014). In order to accommodate high-throughput chemical assessments, SHEDS-Multimedia has been numerically and operationally modified to reduce user burden and increases run speed. The SHEDS-HT model uses a dynamic fugacity-based source-to-concentration module to estimate indoor concentrations by media (air, dust, and surfaces) for chemicals with indirect exposure scenarios, while direct scenarios (exposure during product use) are addressed via appropriate exposure equations. The concentration estimates, relevant exposure factors, exposure predictions, and human activity data are then used by the SHEDS-HT model to rapidly generate population distributions of potential exposures via dermal, non-dietary ingestion, and inhalation pathways. Due to the small sample size of the EPA pilot study add-on, direct comparison of predicted population SHEDS exposures and those measured in the pilot study may not be of use. However, the pilot study will provide a large number of matched product use, indoor media concentration, exposure (e.g., hand wipes), and biomarker measurements that could be used to evaluate individual algorithms or assumptions of the SHEDS-HT model. If the pilot study methods were incorporated into the main Green Housing Study, then direct comparisons between percentiles of predicted exposures and measured metrics could be performed (e.g., for groups with different consumer product use patterns).

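### Product use is recorded only as usual frequency, with no item on use during the Day 1 to Day 5 air sampling, so the planned use-to-air correlation is attenuated for weekly and especially monthly products

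*Protocol*

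**What the plan says.** The add-on questionnaire (Protocol, Appendix C, parts E and F, items 21 and 22) has the instruction "Please select use frequency for each product type inside your home" above 11 cleaning products and 8 personal care products. The four answers are daily, weekly, monthly and yearly/never, with no reference period. Item 23 uses the same scale for broad product classes. Section 4.5 describes the content: "These questions are based on participant recall and cover typical cleaning and personal care activities carried out by any of the household residents".

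The air window is short and fixed. For the passive sampler, which collects the volatile analytes, Section 4.4.1 states: "The tube cap will be removed on the first day of sampling, and will be replaced on the return visit on Day 5". For the active sampler, flow is set so that "the pump can run for 5 consecutive days". Table 7 puts the questionnaire on Day 5. Section 4.4.4 confirms that it is "collected on Day 5; questions are answered by participants for activities and locations for the preceding day, i.e., Day 4".

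Table 8 plans, for Objective 5, a comparison of product categories reported as used with chemicals found in media, including "correlation of magnitude with reported use frequencies". The Objective 5 text in Section 5.0 describes the data as "matched product use, indoor media concentration, exposure (e.g., hand wipes), and biomarker measurements". Objective 4 combines the frequency answers with the inventories to predict residential concentrations, and evaluates this for indicator chemicals against measured values. Objective 1 regresses analyte measurements on product variables, among others.

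**The concern.** The outcome belongs to one window of four to five days. The predictor is a habit with no time frame. A home that ticks monthly and did not use the product that week is treated as a user, while its air sample contains nothing from that product. Some weekly homes are in the same position.

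Nothing else on the form fills the gap. The recall grid for the previous day records the child's locations and activities, not products. The consumer product inventory is taken on Day 1 and shows what is stored, not what is used. Yet the caregiver is interviewed on the day the samplers are collected, when use in the window could easily be asked.

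At stake is how Objectives 1, 4 and 5 read for air. A real product effect on limonene or linalool could look weaker than it is, and a model algorithm could look worse than it is. Use in the window cannot be recovered later from the stored data.

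**Working it through.** The protocol gives no power or probability for this correlation, so there is no figure to reproduce.

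**Step 1. Chance that a product is not used in the window.** Inputs: window W = 4 days (Day 1 to Day 5, same clock time) or 5 days (five calendar days), from Section 4.4.1 and Table 7; interval between uses T = 7 days for weekly and 30 for monthly, from the answer scale. Regular use with random phase gives P(no use) = 1 − W/T. Irregular (Poisson) use gives exp(−W/T).

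| Answer | Regular, W=4 | Regular, W=5 | Irregular, W=4 | Irregular, W=5 |
|---|---|---|---|---|
| Weekly | 1−4/7 = 42.9% | 1−5/7 = 28.6% | exp(−4/7) = 56.5% | exp(−5/7) = 49.0% |
| Monthly | 1−4/30 = 86.7% | 1−5/30 = 83.3% | exp(−4/30) = 87.5% | exp(−5/30) = 84.6% |

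Daily products are used in 98 to 100% of windows. Frequency class is thus a good stand-in for daily use, a rough one for weekly use and a poor one for monthly use.

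**Step 2. Effect on the planned correlation (illustrative).** From the protocol: 64 homes (32 + 32, Section 2.1). Assumed: uses in the window follow a Poisson distribution with mean W/T; yearly/never means once in 365 days; concentration = (1 + 5 × uses per day) × lognormal error with geometric SD 2 or 3; only use in the window contributes; recall is without error; two-sided 5% test, one visit. Ranges run over W = 4 to 5 and geometric SD 2 to 3.

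| Homes | Spearman, frequency class | Spearman, in-window count | Power, class | Power, count |
|---|---|---|---|---|
| Equal thirds weekly, monthly, yearly/never | 0.13–0.21 | 0.29–0.43 | about 18–38% | about 66–96% |
| Equal quarters, with daily added | 0.44–0.59 | 0.54–0.71 | about 95–100% | near 100% |

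Grouping the count as 0, 1, 2–3, 4 or more leaves the correlations practically unchanged.

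**Step 3. Sensitivity to the emission multiplier.** With no daily users and W = 4, moving the multiplier from 2 to 10 takes power from 9 to 54% for class and from 26 to 100% for count. The direction is stable; the size depends on the assumptions.

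**Step 4. Which media share the window.** Table 6 lists consumer-product ingredients in indoor air, dust, surface wipe, urine and duplicate diet, but not in hand wipes. Table B-1 adds hand wipes only if resources allow. Table 7 puts surface wipes on Day 1 and sibling urine on Days 3 and 4. Only the air samples match a Day 1 to Day 5 count.

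**The case against.** A reader might infer that most weekly and monthly products go unused in the window, so that the plan misses real links. The documents do not support this. A product used regularly once a week is used in 57 to 71% of windows. Only monthly products are mostly unused. The link is attenuated, not lost.

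The large power gap also depends on having no daily users. Daily is the first answer offered, and the list includes shampoo and liquid hand soap. Where many homes use a product daily, frequency class already has ample power.

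The add-on collects data at four visits (Section 4.1), and usual frequency predicts a multi-visit average better than a single sample. If half the error variance lies between homes, averaging four visits gives about 0.52–0.65 with class against 0.56–0.70 with count when a quarter use the product daily, and about 0.18–0.27 against 0.24–0.37 with no daily users (W = 4). The gap narrows but does not close.

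Much of the planned use of these answers is sound. Objective 5 covers dust and surface wipes as well as air, and usual frequency is a natural exposure-model input. Section 5.0 itself says that direct comparison of predicted population exposures with measurements may not be useful at this sample size. A caregiver's count of uses by all residents will contain error, which the simulation ignores. Objectives 4 and 5 are secondary, and this is a pilot of low-burden methods.

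All of this limits the point. It does not remove it for a single visit's air sample and products used weekly or less.

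**Conclusion.** The point stands in limited form. Items 21 and 22 record usual use only, no item shown covers Day 1 to Day 5, and the plan correlates concentrations with those answers. For volatile ingredients in air the attenuation is moderate for weekly products, strong for monthly products, and of little consequence for power where many homes use the product daily.

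The non-use percentages follow from the window and the answer scale under regular or Poisson use. The correlations and powers are illustrative. They rest on an assumed mix of homes, emission multiplier and error, on emission only within the window, and on error-free recall. The parent study's forms are not fully shown, so the statement about missing items is limited to the questionnaire in Appendix C. This is a cheap improvement worth making; it does not invalidate Objectives 1, 4 or 5.

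**What to change.** Add one answer column to items 21 and 22: times used since the Day 1 visit, with answers 0, 1, 2–3, 4 or more. Name this count as the predictor for the Day 1 to Day 5 air samples in Objectives 1, 4 and 5.

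Keep usual frequency for settled dust, Day 1 surface wipes, multi-visit averages and SHEDS-HT inputs. Do not apply the count to hand wipes. Use it for the Day 3–4 urine only if the recall period is limited to the days before the void, since a count up to Day 5 includes uses after the sample.

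Cost: 19 extra answers (11 + 8 product rows), about two minutes of caregiver time per visit by estimate, and a minor amendment to the form. No extra visit or sample is needed.
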